## **4.1.2 Primary Efficacy Measure**

### **4.1.2.1 Time to beginning of relief based on Overall VAS**

The time to beginning of relief will be assessed using the Overall VAS score, where time of beginning of relief will be assessed as the first time point at which the VAS score decreases by at least 20mm at any eligible anatomical location compared to Baseline, with persistence of the decrease at the next time point.

The time of relief will be the first time point at which the Overall VAS score decreases by at least 20mm compared to Baseline. For example, if this was achieved at 2 hours with persistence shown at 4 hours then the time of beginning of relief of symptoms will be 2 hours.

Patients who do not have beginning of relief during the time that they are followed-up will be censored at the last time at which the Overall VAS score is recorded at any eligible anatomical location. Note: If a patient was randomized but did not have any post-baseline efficacy data then they will be censored at Presentation. Patients who first have a decrease of  $\geq 20$ mm at the last time Overall VAS score was recorded will not have achieved beginning of relief with persistence. Therefore, they will be censored at the penultimate time that Overall VAS was recorded.

Time to beginning of relief (minutes) will be calculated as:

Actual date and time of first relief (or date and time of censoring) – Date and time of the Baseline Overall VAS assessment

The actual date and time of beginning of relief will be used in the calculation.

The beginning of relief assessed using Overall VAS will be assessed for the first eligible location at which time to beginning of relief of symptoms by Overall VAS first occurred. Only locations with a populated start date and time and corresponding Overall VAS will be used for the calculation of time to beginning of relief.

For the evaluation of persistence, the decrease of  $\geq 20$ mm is required at the next assessment time for which the Overall VAS score is not missing. For example, if 2 Overall VAS determinations with  $\geq 20$ mm decline from Baseline are separated by a missing scheduled assessment then beginning of relief with persistence would have still been achieved.

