## **4.1.3 Secondary Efficacy Measures**

### **4.1.3.1 Time to minimal symptoms based on Overall VAS**

The time of minimal symptoms for an attack assessed using the Overall VAS is defined as the time at which the Overall VAS score falls below 20mm for all locations where VAS Scores are recorded.

- Patients who do not have minimal symptoms during the time that they are followed-up will be censored at the last time at which an Overall VAS score is recorded. Note: If a patient was randomized but did not have any post-baseline efficacy data then they will be censored at Presentation.
- A worst-case scenario will be used to impute missing Overall VAS scores for locations. If there are 2 non-missing values either side of missing value(s) then last observation carried forward (LOCF) or next observation carried backward (NOCB) will be used to carry forward or back the largest Overall VAS. If there is only one Overall VAS followed by missing values or after missing values it will be carried forward or back. If the Overall VAS score for a location is blank at Baseline, but then the location is affected by angioedema

post-dosing, a score of 0 will be imputed for all post-baseline time-points up until the first documented Overall VAS score. The worst-case scenario method will then be applied for all subsequent missing Overall VAS scores.

- The time to minimal symptoms for patients who receive disallowed concomitant medication will be censored at the last time at which the patient had an Overall VAS score prior to their receipt of disallowed concomitant medication. If this is Presentation and hence prior to study drug administration then the time to minimal symptoms will be censored at time 0 minutes.

Time to minimal symptoms (minutes) will be calculated as:

Actual date and time of minimal symptoms (or date and time of censoring) – date and time of the Overall VAS assessment at Baseline

Time of the actual date and time of minimal symptoms will be used in the calculation.

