#### **4.1.4 Exploratory Efficacy Measures**

##### **4.1.4.1 Time to beginning of relief based on IS score**

The time to beginning of relief will be assessed using the IS scores, where time of beginning of relief will be assessed as the first time point at which the investigator assesses the severity of an attack as at least one point less (IS decreased by at least 1 point) compared to Baseline at any eligible location.

Patients who do not have beginning of relief during the time that they are followed-up will be censored at the last time at which the IS score is recorded for any eligible location. Note: If a patient was randomized but did not have any post-baseline efficacy data then they will be censored at Presentation.

Time to beginning of relief (minutes) will be calculated as:

Actual date and time of first relief (or date and time of censoring) – Date and time of the Baseline IS assessment

The actual date and time of beginning of relief will be used in the calculation.

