##### **4.1.4.2 Time to minimal symptoms based on IS score**

The time of minimal symptoms for an attack using the assessment by the investigator is defined as the time at which the IS at the last location falls to 1 point or below.

The time to minimal symptoms for an attack assessed using the IS scores will be assessed for all locations where IS scores are recorded.

- Patients who do not have minimal symptoms during the time that they are followed-up will be censored at the last time at which the IS score is recorded. Note: If a patient was randomized but did not have any post-baseline efficacy data then they will be censored at Presentation.
- A worst-case scenario will be used to impute missing IS scores for locations. If there are 2 non-missing values either side of missing value(s) then LOCF or NOCB will be used to carry forward or back the largest IS score. If there is only one IS score followed by missing values or after missing values it will be carried forward or back. If the IS score for a location is blank at Baseline, but then the location is affected by angioedema post-dosing, a score of 0 will be imputed for all post-baseline time-points up until the first

documented IS score. The worst-case scenario method will then be applied for all subsequent missing IS scores.

- The time to minimal symptoms for patients who receive disallowed concomitant medication will be censored at the last time at which the patient had an Overall VAS score prior to their receipt of disallowed concomitant medication. If this is Presentation and hence prior to study drug administration then the time to minimal symptoms will be censored at time 0 minutes.

Time to minimal symptoms (minutes) will be calculated as:

Actual date and time of minimal symptoms (or date and time of censoring) – Date and time of the IS assessment at Baseline

The actual date and time of minimal symptoms will be used in the calculation.

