#### **4.1.4.3 Time to beginning of relief based on TEQ**

Time to beginning of relief of symptoms (TEQ) is assessed using Questions 1 and 2 of the TEQ at the most severe eligible location. The time of relief will be the first time point at which the response to Question 1 of the TEQ was 'A Little Better', 'Better' or 'Much Better' AND the response to Question 2 of the TEQ was 'Yes' with persistence of the improvement at the next time point AND the response to Question 2 of the TEQ was 'Yes'). Persistence of the improvement at the next time point can be defined to mean that at the next available time point, the response to Question 1 of the TEQ was at least as good as the previous response (e.g. if the previous response was 'Better' then the subsequent response would have to be 'Better' or 'Much Better', 'A Little Better' would not be sufficient)

The time of relief of symptoms will be the first time point at which Question 1 of the TEQ was 'A Little Better', 'Better' or 'Much Better' AND the response to Question 2 of the TEQ was 'Yes'. For example, if this was achieved at 2 hours with persistence shown at 4 hours then the time of beginning of relief of symptoms will be 2 hours.

In addition, any patient who did not have beginning of relief of symptoms during the time that they are followed-up will be censored at the last time at which the TEQ is recorded for the primary attack location. Note: If a patient was randomized but did not have any post-baseline efficacy data then they will be censored at Presentation.

Patients who do not have a response of 'A Little Better', 'Better' or 'Much Better' to Question 1 of the TEQ and a response of 'Yes' to Question 2 of the TEQ until the last time the TEQ was recorded will not have achieved beginning of relief with persistence. Therefore, they will be censored at the penultimate time that the TEQ was recorded.

Time to beginning of relief of symptoms (minutes) will be calculated as:

Actual date and time of first relief of symptoms (or date and time of censoring) – Date and time of first Study Drug Administration

The actual date and time of beginning of relief of symptoms will be used in the calculation.

To allow for missing data in the calculation of time to beginning of relief of symptoms the following rules will be applied. These will ensure that for each patient a conservative approach to estimating missing data is used:

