#### **4.1.4.5 Time to complete resolution**

In a diary, dispensed at discharge from the hospital, the patient will be asked to record the date and time at which all angioedema symptoms at all locations have resolved (complete resolution). If needed, depending on the patient's level of understanding, parents may assist in completion. During the Day 28 follow-up visit, the date and time of complete resolution of symptoms, as reported by the patient in the diary, is then recorded in the Day 28 CRF.

Time to complete resolution of all symptoms at all locations will be assessed using the answer recorded on the CRF.

- Time to complete resolution of symptoms will be defined as 'Time HAE attack resolved' on the CRF.
- Patients who do not have complete resolution of symptoms during the time that they are followed-up will be censored at 72 hours if the patient confirms that they did not have complete resolution of symptoms during the follow-up time, or at the time of discharge if the 'Date HAE attack resolved' and 'Time HAE attack resolved' on the CRF were not completed. 72 hours is chosen as this is the average length of time that swelling would be expected to subside without treatment. Note: If a patient was randomized but did not have any post-baseline efficacy data then they will be censored at Presentation.
- The time to complete resolution of symptoms for patients who receive disallowed concomitant medication will be censored at the last time the patient had an Overall VAS

score prior to their receipt of disallowed concomitant medication. If this is Presentation and hence prior to study drug administration then the time to complete resolution of symptoms will be censored at time 0 minutes.

Time to complete resolution of symptoms (minutes) will be calculated as:

Actual date and time of complete resolution of symptoms (or date and time of censoring) –  
Date and time of Study Drug Admin

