#### **4.1.4.6 Therapeutic failure**

A patient will be assessed as having had a therapeutic failure if any of the following occurs:

- Time to the beginning of relief of symptoms for the attack based on the Overall VAS occurs later than 4 hours after Baseline.
- Within 4 hours after beginning of treatment administration and after beginning of relief, the Overall VAS increases again to a value of at least the Baseline score.
- The patient has occurrence of HAE at a new location within 4 hours after achieving beginning of relief of symptoms (Based on an IS score of greater than 0 at a new location that had an IS score of 0 at Baseline). Beginning of relief of symptoms here is based on the Overall VAS as defined in Section 4.1.2.1.
- The patient taking any of the medications that may interfere with the assessment of the impact of Ruconest on efficacy measures, between the onset of the attack and prior to time of initial relief of symptoms including:
  - Narcotics
  - Plasma-derived C1 inhibitor
  - Fresh frozen plasma
  - Bradykinin receptor antagonist
  - Analgesics
  - Anti-emetics
  - Non Steroidal Anti-Inflammatory Drugs (NSAIDs)
  - Paracetamol (within 45 minutes before the administration of Ruconest)

The medical monitor will perform a manual review of the concomitant medications and identify those which fall into the above categories.

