## **5.5 Handling of Missing Data**

### **5.5.1 Efficacy Endpoints**

For the time to event efficacy endpoints, if there is insufficient data to ascertain whether a patient has had an event, it will be assumed that they have not had the event.

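### Time to beginning of relief has no rule for disallowed medication, so an attack that improves after another drug counts as relieved although the plan classes it as a therapeutic failure

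*SAP*

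**What the plan says.** **Time to beginning of relief (TTBR).** SAP 4.1.2.1, headed as the primary efficacy measure, sets the event at "the first time point at which the VAS score decreases by at least 20mm at any eligible anatomical location compared to Baseline", persisting at the next non-missing assessment. It censors attacks with no relief, with no post-baseline data, or with the fall first seen at the last VAS. SAP 4.1.4.1 sets the IS version at the first time "the investigator assesses the severity of an attack as at least one point less (IS decreased by at least 1 point) compared to Baseline". For the TEQ version, SAP 4.1.4.3 says "The time of relief of symptoms will be the first time point at which Question 1 of the TEQ was" one of the three improved answers, with a yes to Question 2. None of the three mentions medication. Nor do the protocol definitions in 10.1.2, 12.2 and Appendix F.

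**Time to minimal symptoms (TTMS) and complete resolution.** These four endpoints do have a rule. SAP 4.1.3.1 says that TTMS "for patients who receive disallowed concomitant medication will be censored at the last time at which the patient had an Overall VAS score" before the medication. SAP 4.1.4.2 opens the same way, "The time to minimal symptoms for patients who receive disallowed concomitant medication will be censored at the last time", and 4.1.4.4 repeats it for the TEQ. SAP 4.1.4.5 treats complete resolution likewise, in a sentence that begins "The time to complete resolution of symptoms for patients who receive disallowed concomitant medication will be censored at the last time the patient had".

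**Therapeutic failure.** SAP 4.1.4.6 makes an attack a failure if interfering medication is taken "between the onset of the attack and prior to time of initial relief of symptoms including" narcotics, plasma-derived C1 inhibitor, analgesics, anti-emetics and other listed drugs. Protocol 10.1.3 has the same rule. Protocol 8.2.2 applies it to additional treatment other than Ruconest, and allows such treatment after dosing at the investigator's discretion.

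**The concern.** The study has no control arm, so the Kaplan-Meier curves and event percentages are the main description of efficacy. A TTBR event is read as relief after Ruconest. Without a medication rule, relief that follows a narcotic or plasma-derived C1 inhibitor enters the TTBR curve as an ordinary event. The protocol has already decided that such an attack is a failure, so two efficacy tables can describe it in opposite terms, and the TTBR table alone would not show this. Every other time-to-event endpoint has a medication rule. The omission in all three TTBR versions therefore does not read as a declared choice.

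**Working it through.** The plan states no figure to reproduce: no hypothesis test is planned (SAP 5.2) and no sample size was calculated (SAP 2.3).

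**1. Does any general rule fill the gap?**

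| Place in the SAP | What it covers | Reaches a rescued attack with recorded VAS values that improve? |
|---|---|---|
| 5.5.1 | Acts only "if there is insufficient data to ascertain whether a patient has had an event" | No, the data are sufficient |
| 6.7.4 | Censors patients without the event | No, the event rule is met |
| 7.4 | Sets 0 minutes for results already censored for medication before dosing | No, it adds no TTBR censoring |

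**2. One invented attack under the written rules.** Overall VAS is 60, 58, 55, 30, 15, 10 and 5 mm at 0, 30, 60, 120, 240, 480 and 1440 min, with a listed drug at 90 min.

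- TTBR: the fall at 120 min is 60 − 30 = 30 mm, and at 240 min it is 60 − 15 = 45 mm. Both are at least 20 mm, so this is an **event at 120 min**.
- Therapeutic failure: the drug at 90 min precedes relief at 120 min, so this is a **failure**. The later-than-4-hours criterion is not met (120 min is before 240 min).
- TTMS, if the medication rule applies after dosing: **censored at 60 min**, the last VAS before the drug. Without the rule it is an event at 240 min (15 mm, below 20 mm).
- If the drug were instead taken between the 480 and 1440 min assessments, a literal reading of SAP 4.1.3.1 would censor at 480 min, although minimal symptoms were reached at 240 min.

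**3. Possible size (assumed data).** The documents give no rescue rate. Assume *n* = 20 attacks, 2 unrescued non-responders followed to 24 h, and *r* attacks given a listed drug after the 2 h assessment without the event. Of these, *k* then improve persistently. All other attacks are relieved.

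- TTBR by 24 h as written = (18 − r + k)/20.
- TTBR by 24 h with rescue counted as not relieved = (18 − r)/20.
- Difference = k/20, or 5 percentage points per rescued attack that improves.

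| r (all improve, k = r) | As written | Rescue = not relieved | Exact 95% interval for the latter |
|---|---|---|---|
| 0 | 18/20 = 90% | 18/20 = 90% | 68.3–98.8% |
| 1 | 18/20 = 90% | 17/20 = 85% | 62.1–96.8% |
| 2 | 18/20 = 90% | 16/20 = 80% | 56.3–94.3% |
| 4 | 18/20 = 90% | 14/20 = 70% | 45.7–88.1% |

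The case k = r is the extreme. With r = 4 and k = 0, 1, 2, 3 or 4, the as-written figure is 70, 75, 80, 85 or 90%, against 70%. With 0 or 4 unrescued non-responders and r = k = 4, it is 100% against 80%, or 80% against 60%. Medians are the same under both rules in these cases. The upper quartile becomes not reached only at r = 4 in the table (70% is below 75%).

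**4. TTMS, same set, all events after 2 h.** Censoring the rescued attacks at 2 h gives (18 − r)/(20 − r): 17/19 = 89.5%, 16/18 = 88.9% and 14/16 = 87.5% for r = 1, 2 and 4. Counting them as non-events gives 85%, 80% and 70%. If all rescued attacks later reached minimal symptoms and counted as events, the figure would be 18/20 = 90%. The censored estimate lies between the two.

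**The case against.** Endpoints need not all handle rescue the same way. The SAP's TTBR follows the protocol's definition, and the protocol puts the rescue penalty in therapeutic failure. Failures are tabulated by attack with reasons (SAP 6.7.5) and listed beside the time-to-event results (Listing 16.2.6.1.4). TTBR is repeated on the per-protocol set, which may drop some affected attacks if they are judged major violations. Efficacy is a secondary objective with no test, and the protocol lists TTBR among the secondary parameters.

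Most of this stands as a limit on the consequences. It does not remove the point: counting relief regardless of rescue is legitimate only if declared, and here it is undeclared and runs against the plan's own failure rule. The intention-to-treat set is primary for efficacy and keeps these attacks.

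A reader might infer three stronger things that the documents do not support.

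- *That the SAP plainly censors TTMS and complete resolution after post-dose rescue.* SAP 4.1.1.6 words its disallowed list for drugs taken before study treatment. Extending it to later drugs is the most natural reading, because SAP 4.1.3.1 treats Presentation as a special case and protocol 8.2.2 disallows interfering treatment after dosing for as long as possible up to 8 hours. It remains an inference.
- *That censoring TTMS always favours Ruconest.* It does against counting rescue as a non-event. It can be lower than counting later improvement as an event (87.5% against 90% above), and the literal reading that discards earlier events works against the drug.
- *That the bias is known to be large.* No rescue rate is given, and protocol 8.2.2 recommends considering another Ruconest dose first, so four of 20 attacks rescued with other drugs before relief is only an assumption.

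**Conclusion.** The gap is real and covers all three TTBR measures. It matters most for the VAS version, which the SAP labels primary for efficacy. Relative to the protocol's failure rule, TTBR as written is equal or more favourable, never less. Each rescued attack that improves adds 5 percentage points in a set of 20, given full follow-up to 24 h. The actual effect is unknown and is zero if no attack received a listed drug between dosing and relief. Medians did not move in the illustration.

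For TTMS and complete resolution, the censoring is likely informative, since protocol 8.2.2 names progression and unacceptable abdominal pain among the reasons for additional treatment. Its direction depends on the comparator. The point affects how descriptive secondary results are read and leaves the primary safety objective untouched. It is worth correcting because the correction is cheap.

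**What to change.** - **TTBR (VAS, IS, TEQ):** count an attack with a listed medication other than Ruconest before relief as relief not achieved, kept at risk to the last planned assessment (24 h for VAS and TEQ, 4 h for IS). Show the as-written result as a sensitivity analysis.
- **TTMS and complete resolution:** state that events reached before the medication stay events. Report the number of attacks censored for medication, and add a sensitivity analysis that counts them as event not achieved.
- **Reporting:** the SOP deviation form attached to the SAP says the analysis is finalised, and SAP 7.5 sends changes after database lock to the clinical study report. Any re-derivation should be labelled post hoc and justified there.
- **Cost:** the data are already collected (medication times, VAS, IS, TEQ), so the work is re-derivation and report text. Descriptive percentages become slightly less favourable, and a mild drug such as an anti-emetic before relief counts as non-response. The sensitivity analysis shows how much that matters.
- **Separate minor point:** the failure definition in protocol Appendix F lists recombinant human C1 inhibitor before relief, while protocol 8.2.2 excludes Ruconest and protocol 10.1.3 and SAP 4.1.4.6 do not list it. These passages must be reconciled.

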## **4.1.3 Secondary Efficacy Measures**

### **4.1.3.1 Time to minimal symptoms based on Overall VAS**

The time of minimal symptoms for an attack assessed using the Overall VAS is defined as the time at which the Overall VAS score falls below 20mm for all locations where VAS Scores are recorded.

- Patients who do not have minimal symptoms during the time that they are followed-up will be censored at the last time at which an Overall VAS score is recorded. Note: If a patient was randomized but did not have any post-baseline efficacy data then they will be censored at Presentation.
- A worst-case scenario will be used to impute missing Overall VAS scores for locations. If there are 2 non-missing values either side of missing value(s) then last observation carried forward (LOCF) or next observation carried backward (NOCB) will be used to carry forward or back the largest Overall VAS. If there is only one Overall VAS followed by missing values or after missing values it will be carried forward or back. If the Overall VAS score for a location is blank at Baseline, but then the location is affected by angioedema

post-dosing, a score of 0 will be imputed for all post-baseline time-points up until the first documented Overall VAS score. The worst-case scenario method will then be applied for all subsequent missing Overall VAS scores.

- The time to minimal symptoms for patients who receive disallowed concomitant medication will be censored at the last time at which the patient had an Overall VAS score prior to their receipt of disallowed concomitant medication. If this is Presentation and hence prior to study drug administration then the time to minimal symptoms will be censored at time 0 minutes.

Time to minimal symptoms (minutes) will be calculated as:

Actual date and time of minimal symptoms (or date and time of censoring) – date and time of the Overall VAS assessment at Baseline

Time of the actual date and time of minimal symptoms will be used in the calculation.

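### SAP 4.1.3.1 can score a symptomatic location as 0 mm when its VAS forms are missed, giving a false early time to minimal symptoms in a multi-location attack

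*SAP*

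**What the plan says.** Time to minimal symptoms by VAS is the only measure listed under Secondary Efficacy Measures (SAP 4.1.3). The event occurs when the Overall VAS "falls below 20mm for all locations where VAS Scores are recorded". Unlike time to beginning of relief (SAP 4.1.2.1), it need not persist at the next assessment.

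SAP 4.1.3.1 introduces its treatment of missing scores with "A worst-case scenario will be used to impute missing Overall VAS scores for locations". Three rules follow:

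- A gap between two scores takes the larger of the two.
- For a lone score: "If there is only one Overall VAS followed by missing values or after missing values it will be carried forward or back".
- An exception opens "If the Overall VAS score for a location is blank at Baseline, but then the location is affected by angioedema" post-dosing; in that case "a score of 0 will be imputed for all post-baseline time-points up until the first documented Overall VAS score".

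The clock starts at the "date and time of the Overall VAS assessment at Baseline". SAP 4.1.4.2 repeats the exception for the investigator score (IS): "a score of 0 will be imputed for all post-baseline time-points up until the first" documented IS. SAP 5.5.1 sets the general default: where data are insufficient to tell whether a patient had the event, "it will be assumed that they have not had the event".

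**The concern.** The exception has two conditions: no Baseline VAS, and involvement after dosing. It checks neither the Baseline IS, nor the onset time at the location, nor why the form is blank. Under Protocol 10.2.3, VAS forms go to symptomatic locations and extra forms are supplied when a new one appears. A blank can therefore mean that the location was unaffected or that the form was missed.

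If the form was missed, 0 mm is the most favourable value on the scale. It lies below the 20 mm threshold, and because no persistence is needed, one imputed 0 can fix the event time. That is the opposite of the worst case which the paragraph announces. At stake is a time to minimal symptoms that is biased early.

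**Working it through.** The plan gives no figure to reproduce: the sample size rests on feasibility (SAP 2.3) and no test is planned (SAP 5.2). The check applies the imputation text as written to hypothetical two-location attacks, then repeats it without the zero exception, using only the SAP's own larger-neighbour and carry-back rules.

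**Inputs.** Assessments at Baseline, 30 min, 1, 2, 4, 8 and 24 h (SAP 4.1.1.2). Event: both locations below 20 mm (SAP 4.1.3.1). Scores are invented, in mm; times are nominal.

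| Series | A: Baseline; then 30 min to 24 h | B: Baseline; then 30 min to 24 h | With zero rule | Carry-back only |
|---|---|---|---|---|
| 1. B symptomatic at Baseline; Baseline and 30 min missed | 50; 15, 10, 5, 5, 0, 0 | blank; blank, 55, 40, 25, 10, 0 | 30 min | 480 min |
| 2. As 1, with 1 h and 2 h also missed and A slower | 50; 45, 30, 15, 5, 0, 0 | blank; blank, blank, blank, 25, 10, 0 | 120 min | 480 min |
| 3. B new at 45 min; 1 h form missed | 50; 30, 15, 5, 5, 0, 0 | blank; blank, blank, 40, 25, 10, 0 | 60 min | 480 min |
| 4. Only B's Baseline form missed | 50; 15, 10, 5, 5, 0, 0 | blank; 60, 55, 40, 25, 10, 0 | 480 min | 480 min |
| 5. B missed to 1 h, A not yet below 20 mm | 50; 45, 30, 15, 5, 0, 0 | blank; blank, blank, 40, 25, 10, 0 | 480 min | 480 min |

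In series 1 at 30 min, A is 15 mm and B is set to 0 mm, so both are below 20 mm and the event is recorded. Carry-back gives B 55 mm at 30 min, and the first time both are below 20 mm is 8 h (0 and 10 mm).

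**Conditions for a false event.** For a location symptomatic at Baseline, the Baseline form and at least the next form must be missing. For a new location, one missed form after onset is enough. In both cases every other location must already be below 20 mm at that time point. Series 4 shows that a missed Baseline form alone does nothing; series 5 shows the need for the last condition.

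**Effect on the estimate.** With 20 first attacks and no earlier censoring, one extra event moves the Kaplan-Meier estimate at that time by 1/20 = 5 percentage points, until that attack's event would otherwise have counted.

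**Frequency.** Protocol 4.1 puts multi-location attacks at 10 to 15%. The documents give no rate of missed forms; I assume m = 5 to 20% per form. For one given second location with Baseline and 30 min both missed, the chance of at least one such attack in 20 is 1 − (1 − p·q)^20, where p is the multi-location share and q the chance that both forms are missed.

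- Independent misses, q = m²: from 1 − (1 − 0.10 × 0.0025)^20 = 0.5% to 1 − (1 − 0.15 × 0.04)^20 = 11%.
- Second miss always follows the first, q = m: from 1 − (1 − 0.10 × 0.05)^20 = 10% to 1 − (1 − 0.15 × 0.20)^20 = 46%.

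These are upper limits for a false event at that location, since the other must also be below 20 mm. They exclude the new-location route, for which the documents offer no rate.

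**The case against.** The best defence is that the exception was written for new locations. Its wording contrasts a blank Baseline with later involvement, and since forms go to symptomatic sites, a blank Baseline is normal for an unaffected one. Without an exception, carry-back would assign a new swelling's score to times before it existed. All of this stands as intent, and 0 before onset is reasonable. It does not supply the missing condition, and even for a truly new location the rule runs past onset to the first documented score (series 3).

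Several stronger readings are tempting, but the documents do not support them:

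- *A one-location attack with early forms missed is recorded as minimal at 30 min.* The calculation needs the time of the Baseline VAS and the time of the event. With one location and both forms missing, neither exists, and the SAP gives no fallback. In a multi-location attack the other location's forms supply both.
- *The exception contradicts the carry-back rule and SAP 5.5.1.* A specific exception may override general rules. The fair criticism is that, where a form was missed, it points the opposite way from both.
- *The IS version has the same defect in full.* Protocol Appendix F counts a location with a missing Baseline IS as new, so SAP 4.1.4.2 largely follows the protocol. Only the failure to stop at onset carries over.
- *Missed forms concentrate in the youngest or most distressed children.* Nothing in the documents says so. Parents may complete the VAS, and the forms up to 4 h are completed during the hospital stay.

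It is also fair that VAS scores and derived times are listed by patient, so an affected attack could be found on review.

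**Conclusion.** The concern holds in a limited form. As written, SAP 4.1.3.1 can record a false early time to minimal symptoms in a multi-location attack, by either of the two routes shown. In the hypothetical series the event came at 30, 60 or 120 min instead of 480 min. One case shifts an early point of the first-attack curve by about 5 points on 20 attacks; no effect on the median has been shown.

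The series are illustrations, and the frequency rests on assumed miss rates. It is unknown and probably low, because several things must coincide. The study is descriptive, so no error rate is affected. Time to beginning of relief, the SAP's primary efficacy measure, is untouched, because it uses only locations with a recorded start time and a corresponding VAS. This is a minor point, worth correcting because a stated rule gives a wrong value and the data to prevent it are collected.

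**What to change.** In SAP 4.1.3.1, impute 0 only if both conditions hold:

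1. the location was unaffected before dosing (Baseline IS of 0 or not scored, and no recorded onset before dosing); and
2. the time point precedes the recorded onset at that location.

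Otherwise apply the existing carry-back or larger-neighbour rule, or treat the location as not minimal until a score is documented, in line with SAP 5.5.1. In SAP 4.1.4.2, add only the second condition.

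The inputs exist: IS is scored for each affected location, SAP 4.1.2.1 refers to a start date and time by location, and Protocol 10.2.3 has the time recorded when a new location appears. The cost is a sentence in each section, one extra condition in the code, and later event times in any affected attack.

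The SOP deviation form attached to the SAP says that the analysis has been finalised. If so, the practical step is to search the VAS and time-to-event listings (16.2.6.1.1 and 16.2.6.1.4) for the pattern and, if it occurred, to report the corrected times in the clinical study report, where SAP 7.5 places changes made after database lock.
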